9.4. Interim Analysis

An interim analysis may be conducted for internal decision making. Unblinding details would be specified in the unblinding plan section of the SAP or in a separate unblinding document. The SAP will describe any interim analyses in greater detail should they occur.

9.5. Sample Size Determination

Up to approximately 150 participants will be randomized in a **CCI** ratio to LY3526318 and placebo, respectively. It is expected that approximately 85% of participants will complete the double-blind treatment period of the study. **CCI**

CCI

If there is no treatment difference between placebo and LY3526318, the probability of passing the efficacy criterion specified above (i.e., false positive) is approximately 0.1. The simulation for the power calculation and sample size determination was carried out in FACTS Version 6.0.

10. Supporting Documentation and Operational Considerations

10.1. Appendix 1: Clinical Laboratory Tests

The CPMP Master Protocol describes tests that may be performed at additional times noted in the SoA for this ISA. This table describes tests unique for ISA OA02.

Other Tests
LY3526318
concentration
Urine pregnancy

10.2. Appendix 2: Contraceptive and Barrier Guidance

10.2.1. Definitions

Word/Phrase	Definition
Women of childbearing potential	
Females are considered women of childbearing potential (WOCBP) if
 
 • they have had at least 1 cycle of menses, or • they have Tanner 4 breast development. 
Any amount of spotting should be considered menarche. If Tanner Staging of breasts is performed as part of study procedures, please refer to the Reproductive, Pregnancy and Pediatrics Safety Committee Safety Guidance for Children in Clinical Trial regarding Tanner staging.

Women not of childbearing potential	
Females are considered women not of childbearing potential (WNOCBP) if
 
 • they have a congenital anomaly such as Mullerian agenesis • they are infertile due to surgical sterilization, or • they are post-menopausal. 
Examples of surgical sterilization include: hysterectomy, bilateral oophorectomy, or tubal ligation.

Postmenopausal state	
The post-menopausal state should be defined as:
 
 1. A woman at any age at least 6 weeks post-surgical bilateral oophorectomy with or without hysterectomy, confirmed by operative note; or 2. A woman at least 40 years of age and up to 55 years old with an intact uterus, not on hormone therapy*, who has had cessation of menses for at least 12 consecutive months without an alternative medical cause, AND with a follicle-stimulating hormone >40 mIU/mL; or 3. A woman 55 or older not on hormone therapy, who has had at least 12 months of spontaneous amenorrhea, or 4. A woman at least 55 years of age with a diagnosis of menopause prior to starting hormone replacement therapy 
* Women should not be taking medications during amenorrhea such as oral contraceptives, hormones, gonadotropin-releasing hormone, anti-estrogens, selective estrogen receptor modulators (SERMs), or chemotherapy that could induce transient amenorrhea.

Reproductive Toxicology Studies	Embryo-fetal studies are toxicity studies in pregnant animals designed to identify abnormalities in the development of fetuses, which could indicate potential for teratogenicity in humans. The relevant dosing period is during organogenesis.

10.2.2. Contraception Guidance

WOCBP who are completely abstinent as their preferred and usual lifestyle, or in a same-sex relationship, as part of their preferred and usual lifestyle

Must...	Must not...
agree to either remain abstinent, or	
 use periodic abstinence methods 
 calendar ovulation symptothermal, or post-ovulation declare abstinence just for the duration of a trial, or
stay in a same-sex relationship without sexual relationships with males	use the withdrawal method

WOCBP who are NOT completely abstinent as their preferred and usual lifestyle, or in a same-sex relationship, as part of their preferred and usual lifestyle

Topic	Condition
Pregnancy testing	Negative urine result at screening followed by a negative serum result within 24 hours prior to treatment exposure.
	Note: Subsequent pregnancy testing is compound specific.
Contraception	Agree to use 2 forms of effective contraception, where at least 1 form must be highly effective (less than 1% failure rate)

Examples of different forms of contraception

Methods	Examples
Highly effective contraception	
 combination oral contraceptive pill and mini-pill implanted contraceptives injectable contraceptives contraceptive patch (only women <198 pounds or 90 kg) total abstinence vasectomy (if only sexual partner) fallopian tube implants (if confirmed by hysterosalpingogram) combined contraceptive vaginal ring, or intrauterine devices

Effective contraception	
 • male or female condoms with spermicide • diaphragms with spermicide or cervical sponges • barrier method with use of a spermicide 
 ○ condom with spermicide ○ diaphragm with spermicide, or ○ female condom with spermicide 
Note: The barrier method must include use of a spermicide (i.e., condom with spermicide, diaphragm with spermicide, female condom with spermicide) to be considered effective.

Ineffective forms of contraception	
 • spermicide alone • immunocontraceptives • periodic abstinence • fertility awareness (calendar method, temperature method, combination of above 2, cervical mucus, symptothermal) • withdrawal, • post coital douche • lactational amenorrhea

Topic	Guidance
Contraception for men receiving a genotoxic drug and have a female partner of childbearing potential	
 • Agree to remain abstinent (if this is their preferred and usual lifestyle), or • use 1 additional effective method of contraception

The table below describes contraception guidance for all men.

Topic	Guidance
For all men	should refrain from sperm donation for the duration of the study and for the predicted time until estimated plasma levels of partner would be below the level of toxicologic concern, plus 90 days.
Contraception for men with partners of childbearing potential	
 • either remain abstinent (if this is their preferred and usual lifestyle), or • must use condoms during intercourse for the duration of the study, and • for the predicted time until estimated plasma levels of partner would be below the level of toxicologic concern, plus 90 days
Contraception for men in exclusively same sex relationships, as their preferred and usual lifestyle	Are not required to use contraception

Examples of highly effective, effective, and unacceptable methods of contraception can be found below

Methods	Examples
Highly effective contraception	
 • combination oral contraceptive pill and mini-pill • implanted contraceptives • injectable contraceptives • contraceptive patch (only women <198 pounds or 90 kg) • total abstinence • vasectomy (if only sexual partner) • fallopian tube implants (if confirmed by hysterosalpingogram) • combined contraceptive vaginal ring, or • intrauterine devices
Effective contraception	
 • male or female condoms with spermicide • diaphragms with spermicide or cervical sponges • barrier method with use of a spermicide 
 ○ condom with spermicide ○ diaphragm with spermicide, or ○ female condom with spermicide 
Note: The barrier method must include use of a spermicide (i.e., condom with spermicide, diaphragm with spermicide, female condom with spermicide) to be considered effective.

Ineffective forms of contraception	
 • spermicide alone • immunocontraceptives • periodic abstinence • fertility awareness (calendar method, temperature method, combination of above 2, cervical mucus, symptothermal) • withdrawal • post coital douche, or • lactational amenorrhea

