1.3. Schedule of Activities (SoA)

This SoA shows visits and procedures unique to the intervention-specific appendix (ISA) H0P-MC-OA02 for LY3526318. Please refer to the CPMP Master Protocol and the OA DSA H0P-MC-CPMP(1) SoAs for additional information.

	Randomization to ISA	Double-Blind Treatment				Early Discontinuation	Notes
	V3	V4	V5	V6	V7	ED	
Study Week	0	2	4	6	8		
Visit Window (days)		±3					
Physical examination	X		X		X	X	Symptom directed physical exam (see Section 8.2.1) at V5, V7, and ED (if applicable).
Vital signs	X	X	X	X	X	X	At V3, vitals should be taken predose and at approximately 2 and 4 hours post dosing. At V4, V5, V6, and V7, vitals should be taken predose. Pulse rate, respiratory rate, blood pressure, and temperature taken with participant in a sitting position.
ECG			X		X	X	Single ECGs at V5, V7, and ED (if applicable).
Study intervention	X	X	X	X	X		See Section 6.1
Intervention compliance		X	X	X	X	X	
Clinical Laboratory Tests and Sample Collection							
Hematology		X	X	X	X		
Chemistry		X	X	X	X		
Lipid panel		X	X	X	X		
Urinalysis					X		
Urine pregnancy	X	X	X	X	X	X	For all WOCBP at V3: collect sample before dosing.
Urine drug screen	X		X		X	X	See Section 5.3.2 .
HbA1c	X				X	X	

	Randomization to ISA	Double-Blind Treatment					Early Discontinuation	Notes
		V3	V4	V5	V6	V7		
Study Week	0	2	4	6	8			
Visit Window (days)			±3					
PK sample		X	X	X	X	X	X	At V3, samples should be taken at 2 and 4 hours (± 15 minutes) post dosing. At V4, V5, V6 and V7, a sample for PK should be taken before the dose is administered; participants should be asked to refrain from taking their dose on V4-V7 until they have their clinic visit and after the blood sample is taken. The date and time of LY3526318 administration prior to the PK sampling will be recorded, i.e., the dose administered in the clinic at V3 and the last at home dose prior to each of V4, V5, V6, and V7.

CCI

Participant Device

Participant returns device					X	X	CCI	
----------------------------	--	--	--	--	---	---	-----	--

Abbreviations: CCI [REDACTED]; ECG = electrocardiogram; ED = early discontinuation; HbA1c = hemoglobin A1c; ISA = intervention-specific appendix;

PK = pharmacokinetic; V = visit; WOCBP = women of childbearing potential.

2. Introduction

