This intervention-specific appendix (ISA) H0P-MC-OA02 (OA02) is an appendix to the H0P-MC-CPMP (CPMP) Master Protocol and contains unique study elements specific for LY3526318. The master protocol contains the overarching study elements that govern the osteoarthritis (OA) disease-state appendix (DSA) CPMP(1) and this ISA OA02.

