5.1. Inclusion Criteria

Participants are eligible to be included in the study only if all of the following criteria apply:

- [1050] Are men or women who abide by the reproductive and contraceptive requirements provided in OA02 Section [10.2](#), Appendix 2.

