5.2. Exclusion Criteria

Participants are excluded from the study if any of the following criteria apply:

CCI

- [1052] Have an eGFR of less than 30 ml/min/1.73 m², based on the Chronic Kidney Disease Epidemiology Collaboration (CKD-EPI) formula at Visit 1 or Visit 2.

- [1053] Women who are pregnant or breastfeeding.

CCI

CCI

CCI

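### Does the protocol contradict itself on whether the pregnancy test before first dosing uses serum or urine?

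*Protocol*

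**What the plan says.** The OA02 protocol is an intervention-specific appendix (ISA) to a master protocol. Pregnancy testing comes up in five places.

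- **Section 10.2.2.** The guidance has two tables for women of childbearing potential. Only the table for those who are neither wholly abstinent nor in a same-sex relationship has a testing row. It reads "Negative urine result at screening followed by a negative serum result within 24 hours prior to treatment exposure", and a note leaves later testing to the individual compound.
- **Section 1.3.** The legible schedule has one pregnancy row. It is urine, marked at Visits 3 to 7 and at early discontinuation, with the note "For all WOCBP at V3: collect sample before dosing".
- **Section 10.1 (Appendix 1).** The table has two entries, drug concentration and urine pregnancy.
- **Section 5.1, criterion 1050.** Eligible participants "Are men or women who abide by the reproductive and contraceptive requirements provided in OA02 Section" 10.2.
- **Section 5.2, criterion 1053.** This excludes "Women who are pregnant or breastfeeding", with no specimen or time given.

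The protocol also states how far its own schedule reaches: "This SoA shows visits and procedures unique to the intervention-specific appendix (ISA) H0P-MC-OA02 for LY3526318", followed by "Please refer to the CPMP Master Protocol and the OA DSA H0P-MC-CPMP(1) SoAs for additional information". Section 2 sets the hierarchy: "The master protocol contains the overarching study elements that govern the osteoarthritis (OA) disease-state appendix (DSA) CPMP(1) and this ISA OA02".

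**The concern.** First dosing is at Visit 3 (Section 4.1), so the 24-hour window in Section 10.2.2 closes at Visit 3 dosing. At that visit the schedule names urine and Section 10.2.2 names serum. The groups differ as well: the schedule row covers all women of childbearing potential, while the serum requirement covers a subset. Neither the schedule nor Appendix 1 mentions a serum pregnancy test or points to Section 10.2.2.

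The stake is a safety check before exposure to an investigational drug. If the urine row were read as replacing the serum test, a woman in the subset could be dosed without a result that Section 10.2.2 asks for. Because criterion 1050 leads to that section, a monitor might then record an eligibility deviation.

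**Working it through.** No formula applies, and the plan states no figure to reproduce. The check sets the texts side by side.

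**Step 1. Can all the stated tests be done?**

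| Time | Section 10.2.2 (subset) | Section 1.3 (all women of childbearing potential) |
|---|---|---|
| Screening | urine | outside the table, whose first column is Visit 3 |
| Within 24 hours before first dose | serum | urine at Visit 3, before dosing |
| After first dose | left to the compound | urine at Visits 4 to 7 and early discontinuation |

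No cell rules out another. A woman in the subset can have the screening urine test, the serum test and the Visit 3 urine test. A woman outside it has the Visit 3 urine test. No sentence says that urine stands in for serum, or that serum is not taken.

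**Step 2. Does the absence of a serum row mean anything?** It would if these tables were meant to be complete. They are not, as other items show.

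- The key secondary endpoint is the WOMAC pain subscale (Protocol Section 9.1), and SAP Section 6.10.3 says the instrument is given according to the schedule of activities. The legible ISA schedule has no WOMAC row. It has no row for the pain rating behind the primary endpoint either.
- Chemistry is marked at Visits 4 to 7 only. Yet SAP Section 6.12.4 analyses change from baseline in serum creatinine, and exclusion criterion 1052 uses an eGFR "formula at Visit 1 or Visit 2". Some testing before dosing is therefore scheduled elsewhere.
- Section 10.2.1 needs a follicle-stimulating hormone result for one definition of menopause. That test is in neither the legible schedule nor Appendix 1, which is the same pattern as the serum pregnancy test.
- The legible laboratory block of the schedule has 8 rows: hematology, chemistry, lipid panel, urinalysis, urine pregnancy, urine drug screen, HbA1c and the PK sample. Appendix 1 lists 2 of them (PK concentration and urine pregnancy), so 8 − 2 = 6 scheduled tests are not in Appendix 1.

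A missing row is thus weak evidence that a test is not planned. Part of the schedule after the PK row is also redacted.

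**Step 3. Is a tally of missing tests informative?** One could say that 0 of the 2 results named in Section 10.2.2 appear in the legible schedule with the same specimen and time. But the screening test cannot appear in a table that begins at Visit 3, and the serum test may sit in the parent schedules or the redacted part. The tally reflects the table's scope and says little about the plan.

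**Step 4. What happens if the protocol is followed as written?** Criterion 1050 makes Section 10.2 a condition of entry, so a site takes the serum test for the subset. Section 1.3 makes it take urine before dosing for all women of childbearing potential. Both are done.

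**Step 5. How many participants could be involved?** The number in the subset is not given. It lies between 0 and the approximately 150 randomised. No endpoint, analysis set or error rate uses a pregnancy result.

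**The case for a change.** The strongest case for acting is practical. The ISA chose to specify its own pregnancy test before dosing at Visit 3, and someone working from that row gets no hint that Section 10.2.2 names another specimen for some women. The note on compound-specific testing can explain the urine tests at later visits. It does not explain Visit 3, because a test before dosing does not follow exposure. Criterion 1053 does not settle the specimen either. The pointers to the parent documents are general, and none names a serum test. Section 10.4 directs sites to a different disease-state appendix and a different ISA (CPMP(3) and NP02), so text has been carried over without full correction in at least one appendix.

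Part of this stands. The ISA does not say how the Visit 3 urine test and the serum test relate, and a specific cross-reference would make it easier to read. The slip in Section 10.4 is real, but it tells us nothing about whether Section 10.2.2 is out of step with the parent schedules. The risk of dosing on urine alone arises only if a site passes over a requirement that an inclusion criterion sends it to. Two instructions that can both be followed, with their link left unstated, are a gap in signposting. They are not a contradiction.

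**Conclusion.** The texts differ as described, but no contradiction and no missing test is shown, and no change to the plan follows. The point is one of clarity, confined to Visit 3: Section 10.2.2 names serum for a subset, the legible schedule names urine for all women of childbearing potential, and the ISA does not link the two. Followed as written, the protocol delivers both, and all women of childbearing potential have a pregnancy test scheduled before dosing. Sample size, error rates, estimands and efficacy analyses are unaffected.

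This rests on two assumptions: that sites apply criterion 1050 as written, and that the master protocol and the osteoarthritis appendix, which were not available, do not drop or replace the serum test. If they did, the passages would have to be reconciled. Which tests are intended is for the sponsor to say, and this review takes no position on specimen or timing.

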10.3. Appendix 3: List of Excluded Concomitant Medications

CCI

CCI

10.4. Appendix 4: Provisions for Changes in Study Conduct During Exceptional Circumstances

Implementation of this appendix

The changes to procedures described in this appendix are temporary measures intended to be used only during specific time periods as directed by the sponsor in partnership with the investigator.

Exceptional circumstances

Exceptional circumstances are rare events that may cause disruptions to the conduct of the study. Examples include pandemics or natural disasters. These disruptions may limit the ability of the investigators, participants, or both to attend on-site visits or to conduct planned study procedures.

Implementing changes under exceptional circumstances

In an exceptional circumstance, after receiving the sponsor's written approval, sites may implement changes if permitted by local regulations.

After approval by local Ethical Review Boards, regulatory bodies, and any other relevant local authorities, implementation of these exceptional circumstance changes will not typically require additional notification to these groups, unless they have specific requirements in which notification is required (for example, upon implementation and suspension of changes). All approvals and notifications must be retained in the study records.

If the sponsor grants written approval for changes in study conduct, the sponsor will also provide additional written guidance, if needed.

Considerations for making a change

The prevailing consideration for making a change is ensuring the safety of study participants. Additional important considerations for making a change are compliance with Good Clinical Practice, enabling participants to continue safely in the study and maintaining the integrity of the study.

Informed consent

Additional consent from the participant will be obtained, if required, for:

- participation in remote visits, as defined in Section “Remote Visits,”
- dispensation of additional study intervention during an extended treatment period,
- alternate delivery of study intervention and ancillary supplies, and
- provision of their personal or medical information required prior to implementation of these activities.

Changes in study conduct during exceptional circumstances

Changes in study conduct not described in this appendix, or not consistent with applicable local regulations, are not allowed.

The following changes in study conduct will not be considered protocol deviations.

Remote visits

Telemedicine: Telephone or technology-assisted virtual visits, or both, are acceptable to complete appropriate assessments.

Mobile healthcare: Healthcare visits may be performed by a mobile healthcare provider at locations other than the study site when participants cannot travel to the site due to an exceptional circumstance if written approval is provided by the sponsor.

Procedures performed at such visits include, but are not limited to, collection of blood samples, symptom directed physical examinations, ECGs, vital signs, intervention accountability and compliance, AE collection, and collection of health information.

Other alternative locations: Laboratory draws may be done at an alternate location in exceptional circumstances.

In source documents and the CRF, the study site should capture the visit method, with a specific explanation for any data missing because of missed in-person site visits.

Regardless of the type of remote visits implemented, the protocol requirements regarding the reporting of AEs, SAEs, and product complaints remain unchanged.

Every effort should be made to enable participants to return to on-site visits as soon as reasonably possible, while ensuring the safety of both the participants and the site staff.

Local laboratory testing option

Local laboratory testing may be conducted in lieu of central laboratory testing. The local laboratory must be qualified in accordance with applicable local regulations.

CCI

Study intervention and ancillary supplies (including participant diaries)

When a participant is unable to go to the site to receive study supplies during normal on-site visits, the site should work with the sponsor to determine appropriate actions. These actions may include:

- asking the participant to go to the site and receive study supplies from site staff without completion of a full study visit,
- asking the participant's designee to go to the site and receive study supplies on a participant's behalf, and
- arranging delivery of study supplies.

These requirements must be met before action is taken:

- Alternate delivery of study intervention should be performed in a manner that does not compromise treatment blinding and ensures product integrity. The existing protocol requirements for product accountability remain unchanged, including verification of participant's receipt of study supplies.

- When delivering supplies to a location other than the study site (for example, participant's home), the investigator, sponsor, or both should ensure oversight of the shipping process to ensure accountability and product quality (that is, storage conditions maintained and intact packaging upon receipt).
- Instructions may be provided to the participant or designee on the final disposition of any unused or completed study supplies.

Adjustments to visit windows

Whenever possible and safe to do so, as determined by the investigator's discretion, participants should complete the usual Schedule of Activities as described in the CPMP Master Protocol, CPMP(3) DSA, and NP02 ISA. To maximize the possibility that these visits can be conducted as on-site visits, the windows for visits may be adjusted, upon further guidance from the sponsor. This minimizes missing data and preserves the intended conduct of the study.

For participants whose visits have extended windows, additional study intervention may need to be provided to avoid interruption and maintain overall integrity of the study.

Documentation

Sites will identify and document the details of how participants, visit types, and conducted activities were affected by exceptional circumstances. Dispensing/shipment records of study intervention and relevant communications, including delegation, should be filed with site study records.

Source documents generated at a location other than the study site should be part of the investigator's source documentation and should be transferred to the site in a secure and timely manner.

